Our unique combination of pediatric and adult endocrinology skills, laboratory expertise in insulin signaling, and clinical research experience in insulin sensitivity testing in obese youth make us perfectly poised to address these hypotheses. In addition, the use of a longitudinal study design will allow us to examine differences in percent body fat, body fat distribution and changes in BMI over time in the observational arm of the study. It also allows to examine whether treatment of obese children during this time can have beneficial effects on insulin sensitivity and secretion in the treatment arm. Enhancing our understanding of longitudinal changes of insulin sensitivity in obese adolescents and the response to metformin will help us identify potential interventions aimed at the prevention of T2DM.

The studies in this proposal will test the following hypotheses:

HYPOTHESES:

- 1. Obese adolescents, unlike normal weight controls, fail to improve insulin sensitivity at the end of puberty.**
- 2. Treatment of obese adolescents with metformin during puberty will help these individuals result in sustained improvement in insulin sensitivity at the end of puberty, decrease compensatory hyperinsulinemia, and preserve insulin secretion, thereby improving their disposition index (DI).**

To test these hypotheses, we propose to address the following Specific Aims:

SPECIFIC AIM 1 (Observational Arm):

- 1. To compare longitudinal changes in insulin sensitivity and secretion and their correlates in obese and normal weight adolescents during puberty.**
 - a. To compare changes in insulin sensitivity and secretion as measured by frequently sampled intravenous glucose tolerance test (IVGTT) from early puberty to puberty completion between obese and normal weight adolescents.**

- b. To compare changes in body composition, fat distribution, and inflammatory markers over time between these groups.**

Under this Specific Aim, insulin sensitivity and secretion will be measured by frequently sampled IVGTT in early puberty and at puberty completion in obese and normal weight adolescents. Changes in insulin sensitivity will be correlated with changes in inflammatory markers in all participants and body composition in a subset of these participants.

[figure not shown]
SPECIFIC AIM 2 (Treatment Arm):

- 2. To compare changes in insulin sensitivity and secretion and their correlates, in obese adolescents treated with metformin or placebo during puberty.**

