 - a. To compare changes in insulin sensitivity and secretion from early puberty to puberty completion between obese controls and obese adolescents treated with metformin.**
 - b. To compare changes in body composition, fat distribution, and inflammatory markers over time between these groups.**

Under this Specific Aim, obese participants from Specific Aim 1 will be randomized to receive placebo or metformin treatment during puberty. Frequently sampled IVGTT will be performed to measure insulin sensitivity and secretion in early puberty, at the end of puberty when treatment is stopped, as well as six months after treatment completion. Changes in body composition will also be measured in a subset of participants and changes in inflammatory markers will be measured in all participants at these time points.

The nested study design (Fig 1) will efficiently address four important knowledge deficits with a single recruited cohort: 1) Whether obese adolescents recover their pre-pubertal insulin sensitivity at the end of puberty; 2) The relationships between longitudinal changes in insulin sensitivity and changes in body composition in obese and normal weight youth; 3) Whether treatment with metformin during puberty can improve insulin sensitivity in obese adolescents to the level seen in normal weight pubertal adolescents; and 4) Whether treatment of obese adolescents during puberty will result in prolonged improvement of insulin sensitivity and secretion.

Fig. 1

B. BACKGROUND AND SIGNIFICANCE

Insulin Resistance and T2DM in Youth

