We will recruit obese and normal weight subjects who are in early puberty as determined by Tanner staging of breast development and pubic hair in girls and by Tanner staging of pubic hair and estimation of testicular size in the boys. Adolescents whose pubertal status is at least Tanner II (T2), but no more than Tanner III (T3) will be asked to participate. In two studies that assessed insulin sensitivity across all stages of puberty, it was already significantly decreased from prepubertal insulin sensitivity at T2 and, while it had not yet completely recovered in early T5, it was still significantly increased from T4 insulin sensitivity (11;16). We will recruit through our metabolic syndrome and Good Life clinics, through advertisements, and from local pediatric clinics, including Denver Health Medical Center. Because of the ethnic make-up of our clinics, there will be Spanish-speaking only participants included in the study. The study coordinator is a native Spanish-speaker and, therefore, has the ability to consent the participants in Spanish using our consent and HIPAA forms that have been translated into Spanish. Lifestyle intervention materials are also available in Spanish. When the study coordinator is not available, an official Spanish interpreter will be used for the consent process and all study visits. Because of the anticipated high screen-failure rates due to failure to meet physical examination criteria (most notable Tanner staging criteria and BMI criteria), we will need to consent at least 40% more participants than we ultimately intend to enroll. Therefore, we anticipate that 225 participants will need to be consented for screening to be able to enroll 156 participants. The timeline of our experimental approach is shown below (Fig 2). A fasting baseline screening visit, to be performed at the pediatric Clinical Translational Research Center (CTRC), will include assessment of obesity status as determined by height, weight, BMI, waist circumference and hip circumference. An OGTT will be performed in all obese subjects to rule out IGT, IFG and diabetes in all subjects. The following screening labs will also be performed to examine for any significant underlying illness: AST, ALT, electrolytes, CBC, BUN, creatinine, lipids, and urinalysis.

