In adolescence, the number of routine visits to the pediatrician tends to drop. Therefore, we foresee a potential difficulty in recruiting children who are just starting puberty. For this reason, we are including children who are both Tanner 2 and Tanner 3 at study entry. In both of these stages of puberty, insulin sensitivity has been shown to be significantly decreased when compared with Tanner 1 and Tanner 5. The length of time required for progression through puberty varies in individuals. It is important to measure the post-treatment insulin sensitivity in Tanner stage 5, because insulin sensitivity in Tanner 4 may not be significantly different from earlier in puberty and only at T5 insulin sensitivity returns to its pre-pubertal level. For this reason, if a subject has not reached Tanner 5 in two years, they will not have their Study Visit 3 until Tanner 5 has been attained. This means that some subjects may need to be treated for a longer period of time. However, in order to compare differences in insulin sensitivity after treatment is stopped between subjects, the interval from treatment stop (Study Visit 2) to post-treatment follow-up (Study Visit 3), should be consistent.

The natural recovery of pubertal insulin sensitivity may confound measurement of metformin effects on insulin sensitivity as puberty progresses. In order to control for this, we have included a placebo-controlled group and a group of normal weight controls. This will allow us to compare changes in insulin

sensitivity from baseline to the end of puberty between obese treated subjects and both normal-weight and obese subjects who have not been treated.

The length of this study and potential difficulty with attrition are also limitations of this study. To limit the number of participants lost to follow-up, we will maintain frequent contact with participants with quarterly visits for anthropometric measurements, monthly visits for pill-counts and phone contact at least once between these visits. In addition to these visits, the participants in the treatment group will be contacted by telephone at least monthly to inquire about medication side effects and to review changes in diet and exercise. Due to our involvement in the TODAY study and other trials of metformin, our staff are experienced with working on long-term projects with obese and T2DM adolescents, with excellent study retention out as far as four years.

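### The stated question about recovery of pre-pubertal insulin sensitivity goes beyond the design, because nobody is measured before Tanner II; the change-based Hypothesis 1 and Aim 1a remain testable

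*Combined protocol and SAP*

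**What the plan says.** Section A (Statement of Hypotheses and Specific Aims) lists, as the first of four knowledge gaps the nested design will address, "Whether obese adolescents recover their pre-pubertal insulin sensitivity at the end of puberty". The opening of section A uses the same idea: its beta-cell argument turns on obese youth not regaining their sensitivity from before puberty.

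The formal statements are narrower. Hypothesis 1 reads "Obese adolescents, unlike normal weight controls, fail to improve insulin sensitivity at the end of puberty". Aim 1a compares change "from early puberty to puberty completion between obese and normal weight adolescents". Statistical analysis (section D) regresses the 2-year change on group, with sex and the changes in body fat and BMI as example covariates.

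On entry, the Approach to Specific Aim 1 says "Adolescents whose pubertal status is at least Tanner II (T2), but no more than Tanner III (T3) will be asked to participate". Potential Difficulties and Limitations/Alternatives says of both entry stages that "insulin sensitivity has been shown to be significantly decreased when compared with Tanner 1 and Tanner 5".

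On the end of puberty, the protocol says two things:
- Approach to Specific Aim 1, reporting two cited studies: "it was already significantly decreased from prepubertal insulin sensitivity at T2 and, while it had not yet completely recovered in early T5".
- Potential Difficulties: "only at T5 insulin sensitivity returns to its pre-pubertal level". The Rationale for Specific Aim 1 agrees with this.

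Under the Approach to Specific Aim 1, the last IVGTT shared by lean and obese participants is at Tanner V. Only obese participants have another, six months later.

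**The concern.** Return to a pre-pubertal level needs a pre-pubertal value, and the design contains none. If obese controls improve, the data cannot say whether they came all the way back. That distinction is what question 1 asks about and what the rationale in section A rests on. The Background faults the largest earlier study for not comparing obese children at Tanner V with those at Tanner I; this study cannot supply that comparison either.

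Two further points affect how the result is read. If sensitivity is still rising in early Tanner V, a measurement taken then may understate the eventual recovery. And the protocol places the lowest point at Tanner III, so Tanner II and Tanner III entrants start from different points on the curve. Entry stage is not among the covariates named, and obese versus lean is not a randomised contrast.

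**Working it through.** **1. The plan's own power figure.** Inputs from Sample size calculation: 30 per group, SD 1.85, 2-year changes of 1.16 (metformin), -0.17 (obese control) and 1.6 (normal control), two-sided alpha 0.05.
- Grand mean = (1.16 - 0.17 + 1.6)/3 = 0.863.
- Sum of squared deviations = 0.297² + 1.033² + 0.737² ≈ 1.70.
- Noncentrality = 30 × 1.70/1.85² ≈ 14.9, with 2 and 87 degrees of freedom.
- Power = 93.5%, against 93% stated. Reproduced.

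**2. The contrast behind Hypothesis 1 and Aim 1a.** Difference = 1.6 - (-0.17) = 1.77. Standard error = 1.85 × √(2/30) = 0.478. Noncentrality = 1.77/0.478 ≈ 3.71. Power from the noncentral t is 95.4%. The change-from-early-puberty question is adequately powered on the protocol's assumptions.

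**3. The recovery question.** No power or precision can be computed, because the documents give neither a pre-pubertal value nor a recovery criterion. An illustration shows why this matters. Let f be the fraction of pre-pubertal sensitivity already lost at entry. Full recovery then needs a proportional rise of 1/(1 - f) - 1. With f = 0.36 (Background, a clamp comparison of pubertal with pre-pubertal non-diabetics) this is 1/0.64 - 1 = 56%. As f runs from 0 to 0.36, the required rise runs from 0 to 56%. The documents do not give f at Tanner II-III, for obese participants or for minimal-model sensitivity.

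The protocol gives no baseline level either. With f = 0.36 and assumed baselines of 1, 3 and 5 units, full recovery needs rises of 0.56, 1.69 and 2.81. A rise of 1.6, the change assumed for normal controls, would exceed full recovery in the first case, reach 1.6/1.69 = 95% of it in the second and 1.6/2.81 = 57% in the third. The same observed change supports three different conclusions.

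**4. What a null result would say.** If baseline is already lowered, as the protocol states, no rise by Tanner V is evidence against recovery by that time, without any Tanner I value. The ambiguity arises only when obese controls improve.

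**5. Entry stage.** Suppose obese and lean participants follow the same curve relative to their own level, and sensitivity is lower at Tanner III than at Tanner II by d. Change to Tanner V is then larger by d for Tanner III entrants. If p is the share entering at Tanner III, the lean-minus-obese difference in mean change contains (p_lean - p_obese) × d that is due to stage mix alone. The documents give neither p nor d, so the size is unknown. The sign is unfavourable if more obese than lean participants enter at Tanner II: the obese group would then appear to improve less.

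**6. The later IVGTT.** Statistical analysis already plans the mean change from treatment stop to six months later, with a 95% CI. If SD 1.85 applied (an assumption: it was derived for a 3-month change in the cited trial), the half-width for one group of 30 would be 2.045 × 1.85/√30 = 0.69 units.

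**The case against.** The strongest reply is that the formal plan does not depend on the disputed phrase. Hypothesis 1, Aim 1a, the regression and the sample size all concern change from early puberty, and the protocol expects obese controls not to improve (-0.17). Under that result no Tanner I value is needed. All of this stands, and it confines the point to question 1, the matching text in section A and the conclusions drawn from them. A reader might infer that Aim 1 as a whole is unanswerable; the documents do not support that.

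A reader might also infer that the endpoint is fixed at a moment when the protocol concedes recovery is incomplete. That too is more than the text bears. Incomplete recovery rests on a single statement about early Tanner V, against others placing the return at Tanner V. Nor is the visit clearly at first Tanner V. The Approach to Specific Aim 1 ties it to reaching that stage, while the Approach to Specific Aim 2 describes a two-year period, extended if Tanner V has not been reached, so some participants could be measured later within it. These passages need reconciling; they do not establish a flawed endpoint.

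Nor does any passage say that incomplete recovery will be reported as failure. Lean controls are tested at the same stage, so a lag would tend to affect both groups. And the six-month change with its CI is already planned, so only its use here is new.

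Adjusting for entry stage supplies no pre-pubertal reference. That is true, but the adjustment serves the contrast that remains testable.

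**Conclusion.** The point holds in limited form. The study can show whether insulin sensitivity improves from Tanner II-III to Tanner V and whether that differs by weight group. It cannot show whether obese adolescents recover their pre-pubertal sensitivity if they improve at all. This rests on the protocol's own statements that entry-stage sensitivity is already reduced and on the absence of any Tanner I value or reference. It does not depend on the 36% and 56% figures, which are illustrative and should not be read as an estimate of the unclassifiable range in this population.

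The disagreement over Tanner V is an inconsistency to resolve. Until it is, a statement that obese adolescents failed to recover needs qualification. The entry-stage concern has a known direction for a given imbalance but an unknown size. No stated power figure changes.

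**What to change.** 1. Reword question 1 and the related text opening section A to match Aim 1a: whether insulin sensitivity improves from Tanner II-III to Tanner V, and whether that improvement differs between obese and normal-weight adolescents. Drop recovery of pre-pubertal sensitivity as a conclusion.
2. Add entry Tanner stage (II or III), already recorded at screening, as a covariate in the regression under Statistical analysis.
3. Reconcile the Rationale and Approach of Specific Aim 1 with Potential Difficulties on early Tanner V, and the Approach sections of the two aims on when the end-of-puberty visit falls.
4. Report the planned six-month change with its 95% CI separately for the placebo group, and use it to qualify any statement that obese adolescents failed to recover. State that it has no lean comparator: it can warn that sensitivity was still rising but cannot establish recovery.

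No new visit, participant or procedure is needed. The cost is a narrower claim, one more covariate and some editing.

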After determination of eligibility, participants will have a one-day CTRC admission for baseline laboratory studies, IVGTT, and body composition assessment (Study Visit 1) following an overnight fast. Upon arrival they will have an IV placed for blood draws and injections. Fasting blood glucose and insulin will be drawn at this time. Sex steroids and inflammatory markers will also be drawn at this time. (After the blood draw, they will undergo a frequently sampled IVGTT (specific methods for above described after Specific Aim 2). Up to 10 obese subjects will participate in the arm, as pilot subjects, who **are not** part of the treatment arm (i.e. they will not be taking a placebo).

In the afternoon of the Study Visit 1, a dual-energy x-ray absorptiometry (DEXA) scan will be performed to determine body composition. In a subset of participants (13 per group), soleus muscle nuclear magnetic resonance (NMR) and abdominal fast magnetic resonance imaging (MRI) sequence will also be performed to measure body fat distribution in terms of IMCL, liver fat content and visceral adipose content.

The next study visit (Study Visit 2) will occur when the participant has reached Tanner stage IV, approximately one year after the baseline visit. At this time the baseline laboratory draw, imaging studies and IVGTT will be repeated. For those subjects randomized to the MRI, it will not be repeated at this visit.

The next study visit (Study Visit 3) will occur when the participant has reached Tanner stage V, approximately one year after Study Visit 2. At this time the baseline laboratory draw, imaging studies and IVGTT will be repeated. This is the last long visit for the lean subjects. The obese subjects will stop taking the study medication at this time point.

The next study visit (Study Visit 4) will occur 6 months after the obese participants have reached Tanner stage V. At this time the baseline laboratory draw, imaging studies and IVGTT will be repeated. This is the last long visit for the obese subjects. For those subjects randomized to the MRI, it will not be repeated at this visit.

Between the visits, participants will be asked to come in every 6 months for anthropometric measurements and Tanner staging. Obese participants in the treatment arm (randomized to either Metformin or placebo) will also be asked to come in quarterly for pill counts to measure medication compliance and to receive a refill on their medication.

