Lean subjects will be asked to undergo a total of 3 DEXA scans throughout the course of the study, and for those randomized to the MRI, they will be asked to undergo a total of 2 MRI's. Obese subjects will be asked to undergo a total of 4 DEXA scans through the study, and for those randomized to the MRI, they will

Visit Number	Puberty Exam	Height & Weight	Pill Count	OGTT	IVGTT	DEXA	MRI*	Total Time
Screening Visit	x	x		x				4 hr
Study Visit 1		x			x	x	x	5-8 hr
Short Visits (Every 3 months)	x	x	x					1 hr
Study Visit 2	x	x			x	x		5-8 hr
Study Visit 3		x			x	x	x	5-8 hr
Study Visit 4		x			x	x		5-8 hr

be asked to undergo a total of 2 MRI's.

Please see the tables below for a more detailed explanation of the study procedures.

Specific methodology that will be used in this study is described after Specific Aim 2

Treatment table for obese subjects:

*Only those in the group who are asked to have an MRI/MRS

[figure not shown]
No Treatment table for lean subjects/obese pilot no treatment subjects:

Visit Number	Puberty Exam	Height & Weight	OGTT*	IVGTT	DEXA	MRI/ MRS**	Total Time
Screening Visit	x	x	x				2-4 hr
Study Visit 1		x		x	x	x**	5-8 hr
Short Visits	x	x					1 hr
Study Visit 2	x	x		x	x		5-8 hr
Study Visit 3	x	x		x	x	x**	5-8 hr

*Only participants who are overweight

**Only those in the group who are asked to have an MRI/MRS

Fig. 2 Timeline of Study Participation

metformin during puberty will help these individuals recover insulin sensitivity at the end of puberty, decrease compensatory hyperinsulinemia, and preserve insulin secretion, thereby improving their disposition index (DI).

SPECIFIC AIM 2:

2. To compare changes in insulin sensitivity and secretion and their correlates in obese adolescents treated with metformin or placebo during puberty.
 - a. To compare changes in insulin sensitivity, secretion and DI from early puberty to puberty completion between obese controls and obese adolescents treated with metformin.
 - b. To compare changes in body composition, fat distribution, and inflammatory markers over time between these groups.

RATIONALE:

The goal of this aim is to see whether treatment with metformin can improve insulin sensitivity and reduce compensatory insulin secretion during puberty. The thought is that, by improving insulin sensitivity and decreasing insulin secretion requirements during this temporary critical period of reduced insulin sensitivity,

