β -cell function will be preserved. This would make puberty a potential treatment period to target prevention of T2DM.

DESIGN

Participants:

1. 104 Obese participants:
 - a.) BMI \geq 95th percentile
 - b.) Tanner stage II – III at baseline
 - c.) Age \geq 9 years
 - d.) Absence of impaired glucose tolerance (IGT), impaired fasting glucose (IFG) or T2DM, as determined by oral glucose tolerance test (OGTT)

Exclusion criteria:

See Specific Aim 1

Approach:

All obese subjects who are recruited will be randomized after Study Visit 1 to receive metformin or placebo. The 52 participants randomized to the placebo group will then also serve as the obese subjects for the longitudinal observational studies of Specific Aim 1 (Please see Fig 2 for further clarification). In other words, 52 obese participants will be included in both Specific Aims 1 and 2, in order to minimize the total number of participants needed. Randomization will be stratified by: 1) Family history in a first degree relative with T2DM or no family history and 2) BMI between the 95th and 99th percentile or BMI greater than the 99th percentile. The extended release metformin will be started at 500 mg daily for one week and then increased by 500 mg a week until the target dose of 2000 mg a day is attained. The extended release preparation allows patients to take the medication once a day to promote improved adherence and is better tolerated. All obese participants will receive standard lifestyle counseling, focusing primarily on dietary improvements and increased physical activity. The total treatment period will be two years to include, on average, the most resistant stages of puberty. In order to monitor metformin compliance closely, the participants will come in for monthly pill-counts. In addition, each participant will be provided with a pill dispenser and a calendar to record each dose that is taken to assist with and track compliance. Furthermore, parents will be encouraged to remind the participant to take his/her medication. Participants will be given a point each time they bring in their pill bottle, whether or not they have been compliant, and will be eligible for an extra gift card for every 6 points they obtain. Our group has extensive experience in maintaining metformin compliance in this population (52). Tanner staging, anthropometric measurements and lifestyle counseling will also be performed at quarterly visits.

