The CTRC study visit described previously for Study Visit 1 will be repeated twice more: at the end of this treatment period (Study Visit 2) and six months after the treatment is stopped (Study Visit 3). IVGTT, DEXA, abdominal fast MRI and soleus muscle NMR will also be repeated. We anticipate that the majority of patients will be Tanner stage V (T5) at the end of the 2-year treatment period, as the average time from the onset of breast development until menarche is 2-3 years. If T5 has not been reached after two years, the treatment will continue until the individual is at T5. Follow-up visits for Tanner staging will occur quarterly.

The final visit (Study Visit 3) will be to determine whether insulin sensitizing treatment will result in persistent improvement in insulin sensitivity and insulin secretion, even after treatment is stopped. The subjects will again be given a 3-day standard macronutrient diet and will fast overnight prior to admission. Only the IVGTT and anthropometric measurements will be performed at this study visit.

Specific Methods:

Screening laboratory studies: ALT, AST, electrolytes, fasting lipids, CBC, BUN and urinalysis.

Laboratory studies drawn at Visits 1, 2 and (for obese subjects only) 3: sex steroids, c-reactive protein (CRP), interleukin-6 (IL-6), adiponectin and fasting lipids. Sex steroids (free testosterone, estradiol,

androstenedione and DHEAS) will be drawn in order to confirm or refute previously found associations between sex steroids and IR. Inflammatory markers and other factors that have been associated with IR will also be drawn at this visit, including c-reactive protein, interleukin-6, adiponectin and fasting lipids (LDL, HDL and triglycerides).

Anthropometric measurements: Height, weight, waist-to-hip ratio, and supine abdominal height are measured by standard techniques.

Oral Glucose Tolerance Test: Glucose and insulin drawn at fasting (0), and at 30, 60, 120 and 180 minutes after ingestion of glucola (1.75g/kg, max 75g)

Dual-energy X-ray absorptiometry (DEXA Scan): Body composition will be measured supine using the DEXA technique on the pediatric CRC and will be used to derive fat-free mass (92). This technique relies on the absorption of dual electron wavelengths for the assessment of body fat, lean tissue, and bone mineral density.

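### Two incompatible rules fix when obese participants stop study drug and have the end-of-treatment IVGTT, and the Tanner staging intervals also conflict; the effect on Aim 1 is probably small

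*Combined protocol and SAP*

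**What the plan says.** **Endpoint and stop-drug date.** The Approach under Specific Aim 1 makes Tanner V the trigger: "The next study visit (Study Visit 3) will occur when the participant has reached Tanner stage V", and at that visit "The obese subjects will stop taking the study medication at this time point". It then adds: "The next study visit (Study Visit 4) will occur 6 months after the obese participants have reached Tanner stage V". The Approach under Specific Aim 2 uses calendar time: "The total treatment period will be two years to include, on average, the most resistant stages of puberty". It goes on to say that treatment continues past two years in anyone not yet at Tanner V. It does not say what happens when Tanner V comes sooner. There the full study visit is repeated "at the end of this treatment period (Study Visit 2) and six months after the treatment is stopped (Study Visit 3". The section on potential difficulties and limitations repeats the extension for late maturers and is also silent on early ones.

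**Staging interval.** Aim 1 says "participants will be asked to come in every 6 months for anthropometric measurements and Tanner staging", with obese participants also attending quarterly for pill counts. The treatment table for obese subjects has a row headed "Short Visits (Every 3 months" with the puberty exam ticked, and Aim 2 says "Tanner staging, anthropometric measurements and lifestyle counseling will also be performed at quarterly visits". The table for lean and untreated pilot subjects ticks a puberty exam at short visits but gives no interval. The limitations section promises quarterly visits and names only anthropometry.

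**Analysis.** The Statistical analysis paragraph compares a two-year change between groups by linear regression. Its list of confounders is open-ended and names nothing about visit timing.

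**The concern.** The stop-drug date is a dosing instruction for children, and it also sets the date of the endpoint IVGTT. Take a child first staged at Tanner V at 18 months. Under Aim 1 the drug stops and the IVGTT is done at 18 months, with the off-drug visit at 24. Under Aim 2 those dates are 24 and 30 months. Staff cannot tell from the protocol which applies. Participants handled under different rules would differ in treatment length and in time spent at Tanner V when measured.

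Timing within Tanner V can matter. The Aim 1 Approach itself notes that insulin sensitivity has not fully recovered early in that stage. Aim 1 compares lean with obese placebo participants, who are not randomised to those groups, so a systematic difference between them in time into Tanner V can enter the contrast.

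**Working it through.** **Planning inputs** (Sample size calculation): SD of change 1.85; expected changes 1.16 (metformin), -0.17 (obese control) and 1.6 (normal weight); 30 per group; two-sided 0.05. To confirm these are read as the plan uses them:

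- Grand mean = (1.16 - 0.17 + 1.6)/3 = 0.863.
- Sum of squared deviations = 0.088 + 1.068 + 0.543 = 1.698.
- Noncentrality = 30 × 1.698/1.85² = 14.89; with 2 and 87 df the power is 93.5%. The plan states 93%, so the figure reproduces.
- Planned Aim 1 difference = 1.6 - (-0.17) = 1.77; standard error = 1.85 × √(2/30) = 0.478.

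**Stop-drug date.** Aim 1 puts Study Visit 2 about one year after baseline and Study Visit 3 about one year after that, so mean time to Tanner V is about 24 months. The documents give no SD; I assume 4 to 9 months, with a normal distribution. With quarterly staging, the two rules give different dates when Tanner V is first seen at or before 21 months:

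- SD 4: Φ((21 - 24)/4) = Φ(-0.75) = 23%.
- SD 6: Φ(-0.50) = 31%.
- SD 9: Φ(-0.33) = 37%.

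The mean gap among those affected is 3 × [P(T ≤ 21) + P(T ≤ 18) + P(T ≤ 15) + …]/P(T ≤ 21):

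- SD 4: 3 × 0.307/0.227 = 4.1 months.
- SD 6: 3 × 0.5645/0.3085 = 5.5 months.
- SD 9: 7.6 months, after discarding non-positive times.

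A simulation of one million draws agrees. If staging were 6-monthly, the cut-off would be 18 months and the share lower: Φ(-6/4) = 7% to Φ(-6/9) = 25%.

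**Staging interval.** Suppose lean participants are staged 6-monthly, obese participants quarterly, and Tanner V triggers the visit in both. Mean detection delay is half the interval:

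- Lean 3.0 months, obese 1.5 months; difference 1.5 months.
- Slope within Tanner V: not in the documents. Assumed as the planned lean change of 1.6 spread over 24 months (0.067 per month) or over 12 months (0.133 per month).
- Shift = 1.5 × 0.067 = 0.10, or 1.5 × 0.133 = 0.20.
- Relative to plan: 0.10/1.77 = 5.6% and 0.20/1.77 = 11.3%; 0.10/0.478 = 0.21 SE and 0.20/0.478 = 0.42 SE.
- If the true lean-obese difference were zero, a two-sided t-test (58 df) would reject in 5.5% or 7.0% of trials instead of 5%.

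**Both conflicts together.** With a two-year minimum applied to obese participants only and a 24-month mean, the simulated offset runs from lean 0.6 months later to obese 1.3 months later. The direction is therefore not fixed. At the obese controls' planned slope of -0.17/24 = -0.007 per month, moving their visit by 1.3 months changes the contrast by only 1.3 × 0.007 = 0.01.

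**The case against.** Unequal staging is not what any one passage prescribes. Read alone, the Aim 1 text stages everyone 6-monthly. The limitations section, read with the lean table's puberty exam at short visits, can be taken to mean quarterly for everyone. The 1.5-month offset appears only if the 6-month rule is applied to lean participants and the quarterly rule to obese ones. The timeline figure, which might settle the lean interval, is not readable in the available text. All of this stands, and it is why the Aim 1 effect is stated conditionally.

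The two-year period is never called a minimum, so an author could say that Tanner V always governs. But the Aim 2 text sets a two-year period and provides only for lengthening it, while Aim 1 stops drug at Tanner V. Nothing reconciles them.

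A reader might infer that the off-drug interval is broken as well, because Aim 1 times the last visit from Tanner V and Aim 2 from stopping treatment. Applied consistently, either rule gives six months off drug, as the 18-month example shows. Only mixing the rules would shorten the interval. A reader might also treat the visit numbering as a substantive conflict: Study Visit 3 is the Tanner V visit in one place and the off-drug visit in another. The anchoring event is named each time, so this is editorial.

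**Conclusion.** The contradiction in the stop-drug and endpoint date is real, is in the current text, and needs no assumption about insulin sensitivity. Its reach does depend on assumptions: about 23-37% of obese participants, by a mean of about 4 to 8 months, given a 24-month mean, an SD of 4 to 9 months and quarterly staging. Earlier mean times would raise the share, but the Aim 1 timetable points to about 24 months.

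The effect on Aim 1 is probably small: 0.1 to 0.2 against 1.77, on an assumed slope and only under mixed staging. A reader might infer that the plan is tilted towards Hypothesis 1. The documents do not support that, because an obese-only two-year minimum could offset or reverse the staging effect, and the slope within Tanner V is not given. Nor is the randomised comparison biased between arms, since metformin and placebo participants share the same rules. What is left undefined there is treatment length and visit dates for early maturers. The point should be corrected, but it does not threaten the trial's main conclusions.

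**What to change.** 1. Set one Tanner staging interval for all groups and state it in both visit tables. A common 6-month interval adds no visits; Tanner V is then detected about 1.5 months later on average in obese participants than with quarterly staging. A common quarterly interval adds only the exam if the quarterly visits in the limitations section already cover lean participants. If they do not, it adds about four short visits each over two years, at most 4 × 52 = 208.
2. Set one endpoint and stop-drug rule, for example the first staging at Tanner V. If a two-year minimum is wanted, apply it to all groups; the cost is a later endpoint visit for early-maturing lean participants.
3. Time the off-drug visit at six months from the actual stop date, and use one visit numbering. These are text edits.
4. Report time from baseline to the endpoint IVGTT by group. This uses dates already collected.

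Do not rely on a timing-adjusted regression to repair unequal staging. The delay would be about 3 months in lean and 1.5 months in obese participants, nearly collinear with group, so the model could not separate the two. The staging interval has to be made equal by design.
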